8.1 Visit procedures

Procedures and assessments for the scheduled visits are described in this section. The timing of assessments is outlined in the flow chart (Section [2](#)).

If a site visit for some reason is not performed at the scheduled time point, the investigator should arrange for the site visit to be performed as soon as possible and within the scheduled visit windows. Date of visit and visit windows are calculated in relation to randomisation visit (visit 2).

The screening assessments can be performed at any time during the screening period (between visit 1 and 2) as long as all results are available prior to randomisation at visit 2.

At visits after randomisation where it is not possible to perform blood sampling on the actual visit day (e.g. if the child does not cooperate during blood sampling) the samples can be taken within a week from the actual visit. The sampling conditions (fasting or non-fasting) and timing of sampling in relation to trial drug administration, as described in section [8.2](#), should always be followed.

The investigator must keep a subject screening log, a subject identification code list and a subject enrolment log. The subject screening log and subject enrolment log may be combined in one list.

At the information visit (visit 0) the subject will be provided with information regarding the trial and asked to sign the informed consent and child assent form. (Section [18.2](#), [18.3](#)).

At the screening visit (visit 1), subjects will be provided with a card stating that they are participating in a trial and giving contact address(es) and telephone number(s) of relevant trial site staff. Subjects should be instructed to return the card to the investigator at the last trial visit or to destroy the card after the last visit. Each subject will be assigned a unique 6-digit subject number which will remain the same throughout the trial. A screening session must be performed in the IWRS.

8.2 Timing of visits and blood sampling

For the main trial period all blood samples should be collected at the randomisation visit (visit 2) prior to first study drug administration. For cohort II and III subjects who are non-GH treatment naïve, blood sampling at visit 1 and 2 should take place at least 12 hours after the last GH injection. Treatment with marketed product for GHD should discontinue no later than 12 h prior to first trial drug treatment.

In order to assure correct timing of PK and antibody sampling in relation to study drug administration, the visits after randomisation should be scheduled within the allowed visit window according to section [2](#) and the instructions below. Blood samples should always be collected prior to study drug administration if the visit is on a planned dosing day.

For subjects treated with NNC0195-0092

Visit	Timing of visit
3	On a planned dosing day
4	On planned dosing day
5	1-4 days after dosing
6	On a planned dosing day
7	1-4 days after dosing
8	On a planned dosing day
9	1-4 days after dosing
10	On a planned dosing day
11	1-4 days after dosing
12	On a planned dosing day
13	1-4 days after dosing
14	On a planned dosing day
15	1-4 days after dosing
16 ¹	For subjects who have started treatment with a marketed GH product blood sampling should take place at least 12 hours after the last injection.
18	On a planned dosing day
20*	1-4 days after dosing
24*	1-4 days after dosing
28*	1-4 days after dosing
32*	4-6 days after dosing
34	1-4 days after dosing
36	1-4 days after dosing
38	4-6 days after last dosing of trial product

¹ Subjects that discontinue treatment early should perform the follow-up visit at least 7 days after treatment discontinuation.

*Also applicable for subjects enrolled in cohort II and III.

For subjects randomised to Norditropin® FlexPro® visits should be planned according to section [2](#) and [5.3](#).

8.3 Handling of screening failures and treatment discontinuation

8.3.1 Screening failures

If the subject is found to be not eligible to participate in the trial, the subject will be considered a screening failure.

For screening failures the screening failure form in the electronic case report form (eCRF) must be completed with the reason for not continuing in the trial. Serious adverse events (SAEs) from screening failures must be transcribed by the investigator into the eCRF. Follow-up of SAEs must be carried out according to section [12](#).

A screening failure session must be made in the IWRS. The case book must be signed by the investigator in the eCRF.

8.3.2 Re-screening and re-sampling

Re-screening of subjects is allowed ONLY if the screening window of 21 days between visit 1 and 2 is exceeded and the subject was eligible for randomisation. No separate informed consent or child assent is required. At re-screening the subject will receive a new subject ID and all screening assessments and laboratory samples must be repeated except the X-Ray for Bone Age assessment if performed according to section [8.6.5](#). Re-screening is only allowed once.

Re-sampling is ONLY allowed during an unscheduled visit (Section [8.11](#)) if samples are lost or damaged before arriving at the analysing laboratory, or the analysis failed at the laboratory. In case of re-sampling the blood volume to be drawn must be considered. (Section [8.7](#)).

Re-sampling or Re-screening is not allowed if the subject has failed one of the inclusion or exclusion criteria related to laboratory parameters.

8.3.3 Treatment discontinuation

If a subject discontinues treatment with trial product, the investigator must aim to keep the subject in the trial following the normal visit schedule. A treatment discontinuation session must be made in the IWRS and it must be specified in the End of Trial form in the eCRF if the subject will discontinue treatment and participate in subsequent visits or withdraw from the trial.

The following assessments are not applicable for subjects that discontinue treatment with trial product but continue in the trial: Trial drug administration, pharmacokinetics assessments of NNC0195-0092 and Norditropin®, collection of technical complaints and the patient reported outcome questionnaires (only applicable for cohort I) related to treatment burden and preference: Treatment Burden Measure – TB-CGHD-O and TB-CGHD-P and GH-PPQ.

Final drug accountability must be performed. The subject can be switched to a suitable marketed product as described in section [5.4](#). The new medication should be recorded on the concomitant medication form in the eCRF,

Patients that are discontinued from trial product should return the electronic diary at their next contact to the site.

If a subject discontinues treatment before or at visit 5 a follow-up visit (similar to visit 16) should be performed at least 7 days after the end of treatment visit. The subject should only be followed until visit 7. At visit 7 the subject should be withdrawn and the reason for withdrawal “treatment discontinued before or at visit 5” should be entered in the eCRF.

Subjects that discontinue treatment after visit 5 should be followed until the end of the safety extension trial period (visit 15) but should not attend the follow-up visit (visit 16). A follow-up visit (similar to visit 16) should be performed at least 7 days after end of treatment. If subjects discontinue treatment at visit 15, they should perform visit 16. Subjects that continue treatment after

visit 15 (attending the long-term safety extension period) should not attend visit 16 but continue with visit 17 after visit 15. Subjects that discontinue treatment after visit 15 in the long-term safety extension trial period, should come for a last follow-up visit at least 30 days after end of treatment.

For subjects in cohort I, who continue in the extension until NNC0195-0092 is available for prescription for children with GHD or August 2024 at the latest, the following applies:

- Subjects should be treated with NNC0195-0092, █ mg/kg/week until NNC0195-0092 is available for prescription in their country or until August 2024 at the latest.
- The assessments planned for the end of treatment visit defined in the flow chart for cohort I (extension until NNC0195-0092 is available for prescription, [Table 2-4](#)) should be performed at this visit.
- If X-ray and ECG were performed within 6 months prior to the end of treatment visit, these should not be performed at the end of treatment visit. The follow-up visit will take place 30 days after last treatment in the trial, as described in the flow chart ([Table 2-4](#)).

For subjects in cohorts II and III the following applies:

- Subjects should be treated with NNC0195-0092 until August 2024, at the latest.
- The end of treatment visit should be performed August 2024, at the latest.
- The assessments planned for the end of treatment visit defined in the flow chart for cohorts II and III ([Table 2-5](#)) should be performed at this visit.
- If X-ray and ECG were performed within 6 months prior to the end of treatment visit, these should not be performed at the end of treatment visit.
- The follow-up visit will take place 30 days after last treatment in the trial as described in the flow chart ([Table 2-5](#)).

8.3.4 Withdrawals

If the subject is withdrawn, the investigator must aim to perform procedures similar to those for the respective end of trial visit as soon as possible and the follow-up visit. If a bone age assessment was performed within the past 6 months prior to the end of trial visit the assessment should not be performed again.

A treatment discontinuation session must be made in the IWRS. The end-of-trial form must be completed, and final drug accountability must be performed even if the subject is not able to come to the trial site. When data has been source data verified and all queries have been resolved, the case book must be signed by the investigator in the eCRF.

Although a subject is not obliged to give his/her reason(s) for withdrawing from a trial, the investigator must make a reasonable effort to ascertain the reason(s), while fully respecting the subject's rights. Where the reasons are obtained, the primary reason for not completing the trial must be specified on the end-of-trial form in the eCRF.

8.4 Subject related information

8.4.1 Demography

Information about date of birth and sex will be captured in IWRS according to the local regulations. Race and ethnicity will be recorded in the eCRF according to the local regulations.

8.4.2 Concomitant illness and medical history

A **concomitant illness** is any illness that is present at visit 1 or found as a result of a screening procedure.

Any change to a concomitant illness should be recorded during the trial. A clinically significant worsening of a concomitant illness must be reported as an AE according to section [12.2](#).

Medical history is a medical event that the subject has experienced in the past. At least history of GHD and other conditions that the investigator considers relevant to this trial must be recorded.

The following should be recorded in the eCRF:

- History of GHD:
 - Idiopathic or organic GHD
 - Diagnostic method (type of GH stimulation tests) and result of peak GH values (only if applicable)
 - Only required for cohort I and III: Standing height measured minimum 6 and maximum 18 months prior to screening. For cohort I this height measurement is used to assess inclusion criterion 6.
 - Parental height: standing height for both biological parents, either measured or reported (applies to visit 17)
- Concomitant illnesses
- Relevant medical history

The information collected for concomitant illness and medical history should include diagnosis, date of onset and date of resolution or continuation, as applicable.

8.4.3 Concomitant medication

A **concomitant medication** is any medication, other than the trial product(s) which is taken during the trial, from screening (visit 1) to the last visit in the trial. Details of any concomitant medication must be recorded at visit 1. Changes in concomitant medication must be recorded at each visit as they occur.

The information collected for each concomitant medication includes trade name or generic name, dose, frequency, route of administration, indication, start date and stop date or continuation.

If a change is due to an AE, then this must be reported according to section [12.2](#). If the change influences the subject's eligibility to continue in the trial, the monitor must be informed.

After randomisation (visit 2 for cohort II and III) the hormone replacement therapy can be adjusted according to section [8.7.3](#).

8.5 Assessments for efficacy

8.5.1 Body measurements

Body measurements will be assessed according to section [2](#). For children above approximately 2 years standing height should be measured, for children below the age of approximately 2 years, length measurement should be performed.

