End of treatment							x	
Sign off Casebook								x

¹ Visit to be performed when NNC0195-0092 is available for prescription for children with GHD or August 2024, at the latest. Visit 38 will be no later than week 442.

² Visit should take place 1-4 days after trial drug administration.

³ Trial drug should be administered 4-6 days prior to last site visit to ensure wash out prior to antibody test.

⁴ The follow-up visit should take place 30 days after last treatment.

⁵ Collected if performed as per local practice.

⁶ Only for female subjects having menarche during the trial.

⁷ If X-ray and ECG were performed within 6 months prior to the end of treatment visit, these should not be performed at the end of treatment visit.

Table 2-5 Flow chart long-term safety extension trial period (cohort II FOR SWEDEN ONLY not applicable as no subjects will be enrolled into cohort II END OF TEXT FOR SWEDEN ONLY and III FOR INDIA ONLY not applicable as no subjects will be enrolled into cohorts II and III END OF TEXT FOR INDIA ONLY)

Trial Periods	Protocol section	Information for cohort II & III	Screening for cohort II & III	Long-term safety extension trial period																	End of treatment	Follow-up
				1	2	17	18	19	20 ²	21	22	23	24 ²	25	26	27	28 ²	29	30	31		
Visit number		0	1																		32 ^{4,12}	
Timing of visit Weeks		- 1 day minimum	-3 to -2	0	13	26	39	52+1 day	65	78	91	104+ 1 day	117	130	143	156+ 1 day	169	182	195	Last treatment + 5 days	End of treatment + 30 days	
Visit window Days					± 7	± 7	± 7	+ 3	± 7	± 7	± 7	+ 3	± 7	± 7	± 7	+ 3	± 7	± 7	± 7	± 1	+ 2	
Demography	8.4.1		x																			
Medical history ¹	8.4.2		x																			
EFFICACY																						
Body measurements																						
Height/Length	8.5.1.1 / 8.5.1.2		x	x	x	x	x	x	x	x	x	x	x	x	x	x	x	x	x	x		
Body weight	8.5.1.3		x	x	x	x	x	x	x	x	x	x	x	x	x	x	x	x	x	x		
Biomarkers																						
IGF-I	8.7.7		x			x		x		x		x		x		x		x		x	x	
IGFBP-3	8.7.7		x			x		x		x		x		x		x		x		x	x	
PK Sampling	8.7.8			x					x			x		x		x		x		x	x	

Trial Periods	Protocol section	Information for cohort II & III	Screening for cohort II & III	Long-term safety extension trial period																		End of treatment	Follow-up
				0	1	2	17	18	19	20 ²	21	22	23	24 ²	25	26	27	28 ²	29	30	31	32 ^{4,12}	
Visit number		0	1	2	17	18	19	20 ²	21	22	23	24 ²	25	26	27	28 ²	29	30	31	32 ^{4,12}			

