6.3.1 Inclusion criteria (cohort II)

For an eligible subject, all inclusion criteria must be answered "yes", if applicable.

10. Informed consent of parent or legally acceptable representative (LAR) of subject. Trial-related activities are any procedures that are carried out as part of the trial, including activities to determine suitability for the trial. The parent or LAR of the child must sign and date the Informed Consent Form (according to local requirements).
11. Age < 2 years and 26 weeks and a minimum bodyweight of 5 kg **at screening**.
12. Confirmed diagnosis of GHD, the GHD diagnosis must be confirmed by investigator according to local practice.
13. For GH treatment naïve subjects, no prior exposure to GH therapy and/or IGF-I treatment.
14. For GH treatment naïve subjects, IGF-I SDS < -1.0 at screening, compared to age and sex normalized range according to central laboratory measurements.

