8.5.1.1 Standing height

For standing height measurements, European Medicines Agency (EMA) guideline^{[26](#)} should be followed.

A manual for height measurement will be provided to the sites. The use of a calibrated wall mounted stadiometer is mandatory.

Standing height should be measured

- by a trained person blinded to treatment allocation (applicable up to and including visit 16 (week 156) for cohort I) and preferably the same person throughout the trial. Starting from the long-term safety extension (week 156–364), the person performing the height measurement is not required to be blinded, as all subjects are treated with NNC0195-0092 [REDACTED] mg/kg/week.
- preferably by using the same stadiometer
- at the same time (\pm 2 hours, compare to baseline-visit 2) of the day
- without shoes
- with 3 consecutive measurements
- measured in centimetres or inches and rounded to one decimal

The following will be recorded in the eCRF

- date and time of height measurement
- result of height measurement

Confirmation that height measurements have been performed by an independent and trained person should be documented in the subjects medical records.

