8.5.1.2 Length measurement

Length should be measured

- in children up to approximately 2 years by preferably the same person throughout the trial
- preferably by using the same length board
- at the same time (\pm 2 hours, compare to visit 2)
- without clothes (including diaper) and shoes
- with 3 consecutive measurements
- measured in centimetres or inches and rounded to one decimal

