17.4.3 Other analyses

Efficacy

For cohort I, in the first year of the safety extension trial period the derivation formula for HV is: (height at 104 weeks visit-height at 52 weeks visit) / (time from 52 weeks visit to 104 weeks visit in years).

For HV in the second year of the safety extension trial period the derivation formula is: (height at 156 weeks visit - height at 104 weeks visit) / (time from 104 weeks visit to 156 weeks visit in years).

For HV in the first year of long-term safety extension trial period the derivation formula is: (height at 208 weeks visit-height at 156 weeks visit) / (time from 156 weeks visit to 208 weeks visit in years).

For HV in the third year of the long-term safety extension trial period the derivation formula is: (height at 312 weeks visit-height at 208 weeks visit) / (time from 260 weeks visit to 312 weeks visit in years).

For HV in the fourth year of the long-term safety extension trial period the derivation formula is: (height at 364 weeks visit-height at 312 weeks visit) / (time from 312 weeks visit to 364 weeks visit in years).

HV will be calculated for each year in the extension until NNC0195-0092 is available for prescription, in the same way as for the previous years.

For cohort II and III, HV at week 52 the derivation formula is: (height at 52 weeks visit-height at baseline (0 week visit 2) / (time from baseline (0 week visit 2) to 52 weeks visit in years).

For HV in the second year of the long-term safety extension trial period the derivation formula is: (height at 104 weeks visit-height at 52 weeks visit) / (time from 104 weeks visit to 52 weeks visit in years).

For HV in the third year of the long-term safety extension trial period the derivation formula is: (height at 156 weeks visit - height at 104 weeks visit) / (time from 104 weeks visit to 156 weeks visit in years).

For HV in the fourth year of the long-term safety extension trial period the derivation formula is: (height at 208 weeks visit-height at 156 weeks visit) / (time from 156 weeks visit to 208 weeks visit in years).

HV will be calculated for each year in the extension until NNC0195-0092 is available for prescription in the same way as for the previous years.

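### In cohort II, the one annual height velocity that spans the change from length to standing height absorbs any systematic difference between the two methods

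*Combined protocol and SAP*

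**What the plan says.** Section 8.5.1 sets the method by age. On the one side, "For children above approximately 2 years standing height should be measured"; on the other, "for children below the age of approximately 2 years, length measurement should be performed". The instruments differ. For standing height (8.5.1.1), "The use of a calibrated wall mounted stadiometer is mandatory". Length (8.5.1.2) is taken "preferably by using the same length board".

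Cohort II is open to children on both sides of that age; the entry criterion in 6.3.1 reads "Age < 2 years and 26 weeks and a minimum bodyweight of 5 kg". Its flow chart, Table 2-5, places both methods in a single row, "Height/Length", with a value at every treatment visit.

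The velocity derivation in 17.4.3 reads: "For cohort II and III, HV at week 52 the derivation formula is: (height at 52 weeks visit-height at baseline", divided by the elapsed time in years. The later years use the same form. No supplied section contains a conversion between methods, a paired measurement at the changeover, a rule to stay within one method, or a rule to set the value missing.

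**The concern.** A difference between two readings taken by different methods contains true growth plus any systematic difference between the methods. In the changeover year this would look like slower or faster growth. Averaging over children does not remove it, because every crossing interval carries it in the same direction. For many of the youngest children the affected interval would be the first year on trial product, which is the one a reader of the week 52 summary looks at first.

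It may also be hard to repair afterwards. The switch is set only at approximately 2 years, so the visit at which it happens can vary by child and site. The data items listed in 8.5.1.1 are date, time and result; 8.5.1.2 lists none. Nothing in the supplied text asks for the method to be recorded, so crossing intervals might have to be guessed from age.

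**Working it through.** The plan states no figure for cohort II velocity, so there is nothing to reproduce. The check is how an offset passes through the formula.

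**Inputs from the documents**
- Switch at about 2 years (8.5.1); entry below 2 years and 26 weeks (6.3.1).
- Annual visits at week 52 + 1 day and week 104 + 1 day, each with a +3 day window (Table 2-5): days 365 to 368 and days 729 to 732.
- Interval lengths: year 1 is 365 to 368 days; year 2 is 729 − 368 = 361 to 732 − 365 = 367 days.

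**Assumptions (not in the documents)**
- Offset d = length minus standing height, 0.3 to 1.0 cm. If length reads shorter, the sign of the error reverses.
- Baseline age uniform from 0, 0.5 or 1.0 up to 2.5 years; switch at exactly 2 years; all children reach week 52.

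**Which interval crosses**
- Aged about 2 to 2.5 years at baseline: none.
- Aged about 1 to 2: the first year.
- Under 1: the second year.

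So no child has more than one crossing annual interval.

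**Propagation.** With earlier value H0 + d and later value H1, over T years:

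observed velocity = (H1 − H0 − d) / T = true velocity − d / T

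| d (cm) | T = 361/365.25 = 0.988 | T = 365/365.25 = 0.999 | T = 368/365.25 = 1.008 |
|---|---|---|---|
| 0 | 0 | 0 | 0 |
| 0.3 | 0.304 | 0.300 | 0.298 |
| 0.5 | 0.506 | 0.500 | 0.496 |
| 0.7 | 0.708 | 0.700 | 0.695 |
| 1.0 | 1.012 | 1.001 | 0.993 |

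Entries are the error in cm/year: almost one for one with d. On an illustrative true velocity of 10 cm/year (assumed), offsets of 0.3 and 1.0 cm would give 9.7 and 9.0 cm/year, that is 3% and 10% low.

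**Effect on the cohort's first-year mean.** Share crossing in year 1 = 1 year of age divided by the age range:
- from 0: 1/2.5 = 40%
- from 0.5: 1/2.0 = 50%
- from 1.0: 1/1.5 = 67%

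Taking T as 1, the mean shifts by share × d: 0.12, 0.15 and 0.20 cm/year for d = 0.3, and 0.40, 0.50 and 0.67 cm/year for d = 1.0.

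**What the scheduled visits allow.** In year 1, measurements fall at about weeks 0, 13, 26, 39 and 52. If the switch falls in the first or last gap, the longest same-method span is 39 weeks; if in either middle gap, 26 weeks. Annualising multiplies random measurement error by 52/39 = 1.33 or 52/26 = 2 relative to a full year.

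**The case against.** The strongest reply is that the documents nowhere say that the two methods differ. They show only two instruments. The existence, size and direction of an offset are all assumed, and the error figures are little more than that assumption divided by one year. This stands, and it is why the point is conditional.

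The reach is also small. Cohorts II and III together are planned at up to about 30 subjects (6.1.2). Children already measured standing at entry never cross. Enrolment may run until 4 months before the expected last cohort I end-of-treatment visit (5.1), so late entrants may have no annual velocity at all. Safety is the stated aim for these cohorts, efficacy is supportive (3.2), and velocity is summarised descriptively (17.4.3). All of this stands.

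A rule may also exist elsewhere. Section 8.5.1.1 mentions a height measurement manual, and section 17 allows a separate SAP; neither was available, nor was the eCRF. If either holds a rule, 17.4.3 should point to it. One could also read the formula literally, so that a length is not a height and the velocity is undefined. That reading still leaves a rule missing.

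A reader might infer that change in height SDS from week 0 is wrong as well. The documents do not support that. It would carry the offset only if the reference does not distinguish length from standing height, and no reference is named for cohort II; the CDC 2-20 years standard appears as a cohort I entry criterion. A reader might also conclude that crossing intervals should simply be dropped. Under the assumed ages that would remove 40% to 67% of week 52 velocities, selectively in children aged about 1 to 2 at entry.

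**Conclusion.** The point holds as a minor gap in the derivation. In cohort II, a child who enters below about 2 years and stays long enough has one annual velocity that mixes methods. Its error is about d cm/year for an offset of d cm: about 0.3 to 1.0 cm/year under the assumed 0.3 to 1.0 cm, and zero if there is no offset. The shift in the first-year mean depends further on the assumed age distribution.

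It should not be read as a demonstrated bias of known size, or as touching any primary endpoint. The cohort II primary endpoint is adverse events. Cohort I enters at 2 years and 26 weeks or older, and its primary endpoint is based on standing height throughout.

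**What to change.** - In the eCRF, record the method (length or standing) with each value.
- In 17.4.3, flag annual intervals whose two ends were measured by different methods, and summarise them separately from same-method intervals.
- For children with a flagged interval, also report an annualised velocity from the longest same-method span among the measurements already scheduled in Table 2-5, rather than only losing the year.
- State which reference is used for cohort II height SDS and whether it separates length from standing height.

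The cost is one data field, a few sentences in the plan and a little extra analysis, with no added visits. The price is precision: for children who change method, the velocity rests on a shorter span of about 26 to 39 weeks.
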